APPENDIX 1: ABBREVIATIONS

ACTH Adrenocorticotropic hormone

ADL Activities of daily living

AE Adverse event

AESI Adverse event of special interest AlloSCT Allogeneic stem cell transplant

ALP Alkaline phosphatase
ALT Alanine transaminase
ANC Absolute neutrophil count

AR Adverse reaction

ARSAC Administration of Radioactive Substances Advisory Committee

ASCT Autologous stem cell transplant
AST Aspartate aminotransferase

BEAM Carmustine, etoposide, cytarabine, melphalan

BID Twice a day

BM Boehringer-Mannheim test (glucose test)

BMS Bristol-Myers Squibb
BSA Body surface area
BV Brentuximab vedotin

CCL-17 Chemokine (C-C motif) ligand 17

CHI Community Health Index CHL Classical Hodgkin lymphoma

ceCT Contrast enhanced computerised tomography

Cl Chief Investigator

CMR Complete metabolic response
CPA Clinical Pathology Accreditation

CR Complete response CRF Case report form

CT Computerised tomography
CTA Clinical trial authorisation

CTAC CT-based attenuation correction

CTCAE Common Terminology Criteria for Adverse Events

CTSA Clinical Trial Site Agreement

CyTOF Mass cytometry

DHAP Dexamethasone, cytarabine, cisplatin

DICOM Digital imaging and communications in medicine

DRL Diagnostic reference level

DSUR Development Safety Update Report

EBV Epstein-Barr virus ECG Electrocardiogram

ECOG Eastern Cooperative Oncology Group

EDTA Ethylene diamine tetra acetate

EFS Event-free survival

eGFR Estimated Glomerular Filtration Rate

ESHAP Etoposide, methylprednisolone, cytarabine, cisplatin

ESR Expedited Safety Report

EudraCT European Clinical Trials Database

FBC Full blood count

FDG ¹⁸F-Fluorodeoxyglucose

FDG-PET Fluorodeoxyglucose positron emission tomography

FF2F Freedom from second failure Formalin-fixed paraffin embedded **FFPE FISH** Fluorescent in-situ hybridisation

FTP File transfer protocol

FU Follow up

G-CSF Granulocyte colony stimulating factor **GDP** Gemcitabine, dexamethasone, cisplatin

GEP Gene expression profiling **GFR** Glomerular filtration rate **GVHD** Graft-versus-host disease

Haemoglobin Hb

HBcAb Hepatitis B core antibody Hepatitis B surface antibody **HBsAb** Hepatitis B surface antigen **HBsAg**

HBV DNA Hepatitis B virus deoxyribonucleic acid

HCV Ab Hepatitis C virus antibody

Hepatitis C virus deoxyribonucleic acid **HCV DNA HCG** Human chorionic gonadotrophin

HIV Human immunodeficiency virus

HL Hodgkin lymphoma

HMDS Haematological Malignancy Diagnostic Service

HRA Health Research Authority Investigator's Brochure IB

ICE Ifosfamide, carboplatin, etoposide

ICH GCP International Conference of Harmonisation-Good Clinical Practice

IDMC Independent Data Monitoring Committee **IGEV** Ifosfamide, gemcitabine, vinorelbine

Immunohistochemistry **IHC**

IMP Investigational medicinal product

IPEM Institute of Physics and Engineering in Medicine

IR Indeterminate response

ISRCTN International Standard Randomised Controlled Trial Number

IUD Intra-uterine device IUS Intra-uterine system

IV Intravenous

Lactate dehydrogenase LDH LFT Liver function tests LLN Lower limit of normal

MHRA Medicines and Healthcare products Regulatory Agency

MRC Medical Research Council MRI Magnetic Resonance Image

National Cancer Research Institute NCRI

National Health Service NHS No Metabolic Response **NMR** ORR Overall response rate

Overall survival os **OSEM**

Ordered subset expectation maximisation

PD Progressive disease

PD-1 Programmed cell death protein 1 PD-L1 Programmed death ligand 1 PD-L2 Programmed death ligand 2 **PET** Positron emission tomography **PFS** Progression free survival

PI Principal Investigator

PMD Progressive metabolic disease

PML Progressive multifocal leucoencephalopathy

PMR Partial metabolic response

PO By mouth

PR Partial response QC Quality control

REC Research Ethics Committee
RIC Reduced intensity conditioned

ROI Region of interest R/R Relapsed/refractory RS Reed-Sternberg cell

RT Radiotherapy

SAE Serious adverse event
SAR Serious adverse reaction
SCT Stem cell transplant

SPC Summary of Product Characteristics

SUSAR Suspected unexpected serious adverse reaction

SUV Standardised uptake value

TARC Thymus and activation-regulated chemokine

TCR T cell receptor

TRM Treatment-related mortality
TSH Thyroid-stimulating hormone

TMF Trial Master File

TMG Trial Management Group
TSC Trial Steering Committee

UCL CTC CR UK and UCL Cancer Trials Centre

UKAS UK Accreditation Scheme
ULN Upper limit of normal

WOCBP Woman of childbearing potential

APPENDIX 2: QUICK REFERENCE GUIDE TO PATIENT VISITS

Appendix 2.1 Patients who receive Nivolumab

	Before registration	After registration	15-21 days after first or second line salvage	3-6 weeks after first or second line salvage¹	During treatment	End of treatment	FU — 1 month	FU - 2 months	FU - 3 months	FU - 6 months	FU - 9 months	FU - 12 months	FU - Annual	Relapse/Disease Progression
Informed Consent	X													
Medical History	Х			X										
Clinical examination				Χ			Х	Х	Х	X	Х	Х		
Weight				Χ										
Full blood count with differential				X			Х	X	Х	Х	Х	Х		
Biochemistry ²				Х			Х	Х	Х	Х	Х	Χ		
Pregnancy test ³	Х			Χ			Х	Х	Х					
Tests for autoimmune conditions ⁴				Х	See separate		Х	Х	Х					
Thyroid function tests ⁵				Χ	table		Х	Х	Х					
Hepatitis B & C serology ⁶				Χ										
ECG (& echo if indicated)				Х										
Lung function test				Х		X ⁷						Χ		
PET-CT scan (for central review)			Х											
Adverse event assessment					1		Х	Х	Х					
Blood samples for translational research							Х							

Retrieve archival biopsy sample and send to HMDS	Х									
Tumour biopsy; block to be sent to HMDS			X 9 8							X 10 9
Remission status assessment (investigations as per local protocols)					Х	Х	Х	X	Х	
Assessment for late toxicity of nivolumab						Х	Х	Х	Х	

Notes:

- 1 = To avoid subjecting to patients to trial-specific tests unnecessarily, it is strongly recommended to wait for confirmation of PET positivity before undertaking these investigations
- 2 = to include ALT/AST, total bilirubin, alkaline phosphatase, lactate dehydrogenase, urea, creatinine, calcium, albumin, magnesium, sodium, potassium, urate, glucose
- 3 = Women of childbearing potential
- 4 = Amylase, lipase, ACTH
- 5 = (TSH & Free T4; Free T3 to be performed if TSH/Free T4 abnormal)
- 6 = HBsAg, HBsAb (if standard locally), HBcAb, HBV DNA (if HBcAb+), HCV Ab or HCV DNA (use test performed as standard locally)
- 7 = Lung function tests to be performed as soon as possible after decision to stop trial treatment, and before the next line of treatment begins. If patient completes 8 cycles of nivolumab, lung fiunction test should be performed 10 days after last nivolumab administration ±2 days.
- 8 = See section 10.2. To be sent to Weatherall Institute of Molecular Medicine, Oxford
- 9 = End of treatment biopsy to be performed if PET positive after 8 cycles and patient has consented. Block to be sent to HMDS.
- 10 9- Biopsy to be performed at relapse if clinically indicated. Block to be sent to HMDS.

Investigations during treatment

Investigations to be performed within 3 days prior to the start of the cycle unless otherwise stated.

	Beginning of Cycle 1	Beginning of Cycle 2	Beginning of Cycle 3	Beginning of Cycle 4	Cycle 4 day 11-13	Beginning of Cycle 5	Beginning of Cycle 6	Beginning of Cycle 7	Beginning of Cycle 8	Cycle 8 day 11-13
Clinical examination	Х	Х	Χ	Χ		Χ	Χ	Х	X	
Full blood count with differential	Х	Х	Χ	Х		Х	Х	Х	Х	
Biochemistry ¹	X	X	Χ	Х		Χ	Χ	Х	Χ	
Tests for autoimmune conditions ²	Х	Х	Х	Х		Х	Х	Х	Х	
Oxygen saturation	X ³	X ³	X ³	X ³		X ³	X ³	X ³	X ³	
Adverse event assessment	Х	Х	Х	Х		Х	Χ	Х	Х	
Thyroid function tests ⁴	X			Χ				Х		
Pregnancy test (WOCBP only)	X ⁵		Х			Х		Х		
Blood samples for translational research ⁶	Х	Х		Х			Χ		Х	
PET-CT scan (for central review)					Х		7	7	7	Х

Notes:

^{1 =} to include ALT/AST, total bilirubin, alkaline phosphatase, lactate dehydrogenase, urea, creatinine, calcium, albumin, magnesium, sodium, potassium, urate, glucose

^{2 =} Amylase, lipase, ACTH

^{3 =} Immediately prior to administration of nivolumab

^{4 = (}TSH & Free T4; Free T3 to be performed if TSH/Free T4 abnormal)

^{5 =} Pregnancy test must be performed within 24 hours prior to starting nivolumab

^{6 =} See section 10.2. To be sent to Weatherall Institute of Molecular Medicine, Oxford

^{7 =} If patient stops treatment during cycles 5-7, a PET-CT scan should be performed and sent for central review. This should be undertaken at least 11-13 days after last trial treatment administration.

Appendix 2.2 Patients who do not receive Nivolumab

	Before registration	After registration	15-21 days after first or second line salvage	3-6 weeks after first or second line salvage ¹	FU 3 months	FU - 6 months	FU - 9 months	FU - 12 months	FU - Annual
Informed Consent	Х								
Medical History	Х			X					
Clinical examination				X					
Weight				Χ					
Full blood count with				Χ					
differential									
Biochemistry ²				X					
Pregnancy test ³	Χ			Χ					
Tests for autoimmune				Χ					
conditions ⁴									
Thyroid function				X					
tests ⁵									
Hepatitis B & C				X					
serology ⁶									
ECG (& echo if				X					
indicated)				V					
Lung function test				X					
PET-CT scan (for			Х						
central review) Retrieve archival									
		Х							
biopsy sample and send to HMDS		^							
Remission status									
assessment					1				
(investigations as per					X	Х	Χ	Χ	Х
local protocols)									
1 = To avoid subjecting t	n nationt	e to trial-er	L Decific tests	Linnacessari	lly it ic	etronaly	recomm	ended to	wait fo

^{1 =} To avoid subjecting to patients to trial-specific tests unnecessarily, it is strongly recommended to wait for confirmation of PET positivity before undertaking these investigations

HB sAg HBsAb, HBcAb, HBV DNA (if HBcAb+), HCV Ab or HCV DNA

^{2 =} to include ALT/AST, total bilirubin, alkaline phosphatase, lactate dehydrogenase, urea, creatinine, calcium, albumin, magnesium, sodium, potassium, urate, glucose

^{3 =} Women of childbearing potential

^{4 =} Amylase, lipase, ACTH

^{5 = (}TSH & Free T4; Free T3 to be performed if TSH/Free T4 abnormal)

^{6 =} HBsAg, HBsAb (if standard locally), HBcAb, HBV DNA (if HBcAb+), HCV Ab or HCV DNA (use test performed as standard locally)

APPENDIX 3: RESPONSE ASSESSMENT

Modified from:

Role of Imaging in the Staging and Response Assessment of Lymphoma: Consensus Guidelines of the International Conference on Malignant Lymphomas Imaging Working Group (Barrington et al. 2014) and Recommendations for Initial Evaluation, Staging, and Response Assessment of Hodgkin and Non-Hodgkin Lymphoma: The Lugano Classification (Cheson et al. 2014).

Assessable disease

Classical Hodgkin lymphoma is consistently 18-FDG avid. Only lesions that are FDG avid (noting that the first on trial assessment will take place after 2 cycles of first or second line salvage therapy) will be deemed to be assessable lesions for the purposes of this study. The primary assessment of disease response is by PET-CT.

For the purposes of accurate response assessment, the PET-CT scan acquired at the time of establishing the presence of refractory disease or disease relapse (not acquired under study conditions) will be requested for central review alongside the PET-CT scan performed (under study conditions) post 2 cycles of first or second line salvage therapy (or 4 cycles if treated with brentuximab vedotin; PET0).

Complete Metabolic Response (CMR):

Score 1, 2, or 3 with or without a residual mass on 5 point scale 5-PS (Deauville criteria) †

It is recognised that in Waldeyer's ring or extranodal sites with high physiologic uptake or with activation within spleen or marrow (e.g. with chemotherapy or myeloid colony-stimulating factors), uptake may be greater than liver. In this circumstance, complete metabolic response may be inferred if uptake at sites of initial involvement is no greater than surrounding normal tissue even if the tissue has high physiologic uptake;

Bone marrow: No evidence of FDG-avid disease in marrow.

Partial Metabolic Response (PMR):

Score 4 or 5[†] with reduced uptake compared with first study scan and residual mass(es) of any size

Bone marrow: Residual uptake higher than uptake in normal marrow but reduced compared with baseline (diffuse uptake compatible with reactive changes from chemotherapy allowed). If there are persistent focal changes in the marrow in the context of a nodal response, consideration should be given to further evaluation with MRI or biopsy.

Progressive Metabolic Disease (PMD):

Score 4 or 5[†] with either an increase in intensity of uptake in previously identified FDG avid lesions or with additional new FDG-avid lesions consistent with lymphoma

BUT for previously identified FDG-avid lesions, increase in intensity must be accompanied by a change in size that meets criteria for overall progression with >50% increase in overall tumour

burden as measured by SPD of up to 6 lesions at PET4 or PET8 compared with the first scan performed under trial conditions (end of first or second line salvage; PET0).

Growth of one or more existing lesion(s) by >50% with an increase in uptake occurring in the context of a lack of overall progression does not meet the criteria for PMD but is regarded as indeterminate response (IR), see below.

AND new lesions must be consistent with lymphoma and have an identifiable CT correlate.

Indeterminate responses according to the refinement of the Lugano Classification will be documented. For this reason patients will also have contrast enhanced CT scans and combined PET with low dose CT at each response time point, which may be performed at a single imaging session if feasible.

[Note this is a modification of PMD adapted from Cheson et al (2016) to differentiate tumour flare from 'true' PD].

No Metabolic Response (NMR):

Score 4 or 5 with no significant change in FDG uptake from first on study scan [i.e. after 2 cycles of first or second line salvage therapy (4 cycles if treated with brentuximab vedotin); PET0]

Indeterminate Response (IR)

Score 4 or 5 with increase in intensity of uptake in previously identified FDG avid lesions or growth of one or more existing lesion(s) ≥50% at any time during treatment, occurring in the context of lack of overall progression (<50% increase) of overall tumour burden, as measured by the SPD of up to 6 lesions at PET4 or PET8 compared with the first scan performed under trial conditions (end of first or second line salvage; PET0).

[Note this is a modification of IR adapted from Cheson et al (2016) to differentiate tumour flare from 'true' PD].

Patients with IR remain on nivolumab (but are not counted as ORR unless later become CMR/PMR as best overall response).

At reassessment, if PMD confirmed then time point is set at previous designation of IR. PMD will be confirmed at PET8 if the SPD of a total of up to 6 lesions becomes >50% compared to the first scan performed under trial conditions (end of first or second line salvage; PET0).

Ideally biopsy should be performed where possible when lesions designated PET positive (DS 4 or 5) including IR.

Contrast enhanced CT scans (ceCT) will be performed in addition to PET with low dose CT (PET-CT), ideally at the same imaging session or if not possible at a separate imaging session. If performed at the same session, contrast enhanced CT scan should be performed after (low dose) PET-CT.

Management of patients with indeterminate response

Recent evidence suggests that treatment beyond PET-defined progression leads to stable tumour volume reduction in a substantial number of patients (Cohen et al. 2017). Patients with an indeterminate response at PET4 may therefore continue to receive a further 4 courses of nivolumab under the following circumstances:

- 1. The PI judges that it is in the patient's best interests to continue with treatment
- 2. There is no concern that further lesion growth before the next scan (PET8) would cause compression of vital structures or compromise of organ system(s)
- 3. There is no other evidence of tumour progression e.g. recurrence of B-symptoms
- 4. There have been no clinically significant drug related grade 3 or 4 toxicities
- 5. Continuing therapy is discussed with the patient who provides verbal consent this discussion should be documented in the source document.

† Deauville Criteria (5 point scale)

The 5-PS scores the most intense uptake in a site of initial disease, if present, as follows:

- 1. No uptake
- 2. Uptake ≤ mediastinum
- 3. Uptake > mediastinum but ≤ liver
- 4. Uptake moderately higher than liver
- 5. Uptake markedly higher than liver and/or new lesions
- X. New areas of uptake unlikely to be related to lymphoma

Score 4 is uptake greater than the maximum SUV in a large region of normal liver Score 5 is uptake ≥ 3 times the maximum SUV in a large region of normal liver

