Exclusion criteria for trial treatment Deauville score 1-3 after 2 cycles of first or second line salvage chemotherapy (4 cycles if being treated with brentuximab vedotin) Positive serology for hepatitis B or C (some exceptions apply – see sections 6.2.4 & 6.2.5) Active infection requiring systemic therapy Ongoing immunosuppressive therapy, apart from inhaled, intranasal, topical corticosteroids or systemic corticosteroids at low doses (≤10mg prednisolone or equivalent per day). Chemo- or radiotherapy or corticosteroids at a dose of more than 10mg/day prednisolone or equivalent within 14 days prior to response PET-CT. NOTE: corticosteroids can be used AFTER a positive PET-CT scan for symptomatic disease but must be weaned to a dose of prednisolone ≤10mg/day or less (or equivalent) at least 7 days prior to starting nivolumab. Treatment with any investigational agent within 28 days prior to planned start of nivolumab Ongoing grade 2-4 non-haematological toxicities related to prior Hodgkin lymphoma treatments, with the exception of alopecia and grade 2 fatigue Pregnant or breastfeeding women Number of sites: 30 Patients can be consented and registered at any time Treatment summary: before, during or within 14 days after completing two cycles of first line or second line salvage therapy (4 cycles if being treated with brentuximab vedotin). A PET-CT scan will be performed under trial conditions following 2 cycles of first line or second salvage (4 cycles if being treated with brentuximab vedotin) to determine eligibility for trial treatment. Patients who are PET-negative (Deauville 1-3) will not be eligible for trial treatment. They will enter follow up for the purpose of the trial, and any further treatment will be at their treating clinician's discretion. Patients who are PET-positive (Deauville 4-5) after first line salvage chemotherapy will receive 4 x 14-day cycles of nivolumab. A further PET-CT scan will then be performed: Patients who are PET negative (Deauville 1-3) will stop trial treatment and enter follow up. Patients who are PET positive (Deauville 4-5) will have a further 4 x 14-day cycles of nivolumab, unless there is evidence of progressive disease.

ANIMATE

Duration of recruitment:	3 years
Duration of follow up:	Patients will be followed up for a minimum of 3 years. For patients who have been in follow up for more than 3 years, annual survival and disease status follow up will continue until the end of the trial.

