have further management at their treating clinician's discretion and enter follow up for the purposes of the trial. Patients who are PET positive (Deauville score 4-5) will be eligible to receive single agent nivolumab on a 2 weekly intravenous schedule. A repeat PET-CT will be performed after 4 cycles of nivolumab. Patient achieving a negative PET (Deauville score 1-3) after 4 cycles of nivolumab and patients with evidence of progressive disease will stop nivolumab and enter follow up. Further management will be at the treating clinician's discretion, although it is anticipated that most patients will proceed to stem cell transplantation. Patients who remain PET positive (Deauville score 4-5) after 4 cycles of nivolumab, but without evidence of disease progression, will receive up to a further 4 cycles of nivolumab, after which another PET-CT will be performed. Further management will again be at the treating clinician's discretion, regardless of whether the PET-CT is positive or negative, with advice offered in the protocol. The rationale for continuing for 8 cycles is that in the Ansell et al. study (2015), of the patients who responded, only 12 out of 20 had achieved their first response by week 8, suggesting a delayed response in some patients. The rationale for not permitting more than 2 lines of salvage therapy prior to nivolumab, and limiting the number of cycles, is to reduce toxicity of potentially ineffective treatments that might compromise the patient's fitness for SCT.

Use of nivolumab in the salvage setting pre ASCT, rather than after relapse post ASCT, or progression through multiple lines of cytotoxic chemotherapy, is potentially advantageous for a number of reasons.

- Rates of ORR appear to be at least as good as for cytotoxic chemotherapy and BV, despite being tested in a more heavily pre-treated cohort, making nivolumab a very promising rescue salvage regime. This would potentially increase the proportion of patients eligible for ASCT, and reduce the risk of failure of this invasive and costly procedure.
- Using nivolumab in a more upfront context might avoid the need for exposure to multiple successive lines of cytotoxic chemotherapy, which impact negatively on the patient's fitness for ASCT.

There are also theoretical arguments why nivolumab might specifically be preferable to cytotoxic chemotherapy or BV in the salvage setting:

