3. TRIAL DESIGN

This is a single-arm, phase II, multi-centre study of the safety and efficacy of the PD-1 inhibitor, nivolumab, as second-line or third-line salvage therapy as a bridge to stem cell transplant (SCT) in relapsed/ refractory classical Hodgkin lymphoma patients not achieving a complete metabolic response (CMR) on FDG-PET post 2 cycles of first or second line salvage therapy. It will use an Ahern single stage design with independent data monitoring committee review to monitor for safety and efficacy.

Patients with relapsed/refractory classical Hodgkin lymphoma will be registered while undergoing first or second line salvage therapy (first line is preferred). Those eligible for the trial will have a centrally reviewed PET CT scan after 2 cycles of the salvage therapy they are receiving (or 4 cycles if they are undergoing treatment with brentuximab vedotin). Those with CMR on PET CT scan (Deauville score 1-3) will go on to receive further treatment according to the investigator's choice but will be followed up for trial data collection purposes; it is anticipated that most of these patients will proceed to SCT. Those achieving less than CMR on central review of FDG-PET (Deauville score 4-5) will be eligible to receive 4 x 2-weekly nivolumab infusions.

After 4 courses of nivolumab, patients will have an additional centrally reviewed PET-CT scan (PET4). Patients achieving CMR will not receive any further nivolumab, and it is anticipated that most of these patients will proceed to SCT. Those patients with PMR or no metabolic response (NMR) on PET4 can receive a further 4 cycles of nivolumab, again followed by a centrally reviewed PET-CT scan (PET8).

Patients with PMD on nivolumab at any point will stop nivolumab. If a repeat biopsy is obtained to confirm progressive disease histologically, the block should be sent to the HMDS, Leeds.

Further management after PET8 will be at the discretion of the investigator, although it is anticipated that those with CMR or PMR will proceed to SCT. If PET8 shows less than CMR (i.e. PMR or NMR), patients who consent will have a further biopsy to exclude false positive PET signal. The block should be sent to the HMDS, Leeds.

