8.2. Treatment Summary

Patients for whom eligibility for treatment is confirmed (see section 7.2 for details) will receive 4-8 x 14-day cycles of nivolumab. Nivolumab 240mg will be administered on day 1 of each 14 day cycle. Dose banding is not permitted.

Trial treatment should begin within 4 weeks following the PET-CT scan to confirm eligibility for trial treatment (PET0).

	1	2	3	4	5	6	7	8	9	10	11	12	13	14
Nivolumab 240mg IV	Х													

Patients will have a PET-CT scan after 4 cycles (PET4). This should be performed on cycle 4, day 11-13 to allow time for central review before the cycle 5 day 1 visit would be due. Please note that patients must not proceed to cycle 5 prior to receipt of the PET4 central review report.

- If PET-negative (Deauville 1-3), they will stop nivolumab. Further management will be at the discretion of the treating clinician and the patient will be followed up as per the trial protocol (see section 9.6.2).
- If the scan shows disease progression, they will stop nivolumab and have further salvage at their treating clinician's discretion. They will enter into annual follow up for the trial.
- If the scan is positive (Deauville 4-5) but there is no evidence of disease progression, the patient will have a further 4 cycles of nivolumab. Following this, they will be followed up as per the trial protocol (see section 9.6.2).

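### The protocol gives conflicting rules on whether a patient with an indeterminate response at PET4 continues nivolumab

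*Protocol*

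**What the plan says.** Six places in the current protocol text bear on an IR patient at PET4.

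- **Appendix 3, Indeterminate Response:** "Patients with IR remain on nivolumab", and they count in the response rate only if a complete or partial metabolic response follows. No condition or cross-reference is attached.
- **Appendix 3, Management of patients with indeterminate response:** "Patients with an indeterminate response at PET4 may therefore continue to receive a further 4 courses of nivolumab under the following circumstances". Five conditions follow: the PI judges continuation to be in the patient's interest; further growth before PET8 raises no concern about compressing vital structures or compromising organs; nothing else suggests progression; there has been no clinically significant drug-related grade 3 or 4 toxicity; and the patient gives verbal consent after a documented discussion.
- **Section 8.2:** for a Deauville 4-5 scan where "there is no evidence of disease progression, the patient will have a further 4 cycles of nivolumab". IR is not named.
- **Section 1.1:** "Patients who are PET positive (Deauville 4-5) will have a further 4 x 14-day cycles of nivolumab, unless there is evidence of progressive disease". IR is not named.
- **Section 2.1:** patients still PET positive after four cycles "but without evidence of disease progression, will receive up to a further 4 cycles of nivolumab". IR is not named.
- **Section 3:** "Those patients with PMR or no metabolic response (NMR) on PET4 can receive a further 4 cycles of nivolumab". IR is not named.

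**The concern.** One and the same patient is told three things: continues, may continue if five conditions hold, and is not listed among those who may continue. Section 8.2 is where a site looks to decide on cycle 5. It neither mentions IR nor refers to the conditions in Appendix 3.

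Two things are at stake. The first is patient protection. IR means that uptake has increased or a lesion has grown, and two of the conditions deal directly with that situation: the compression check and the renewed consent discussion. The second is the primary endpoint. An IR patient counts in the overall response rate only after a later complete or partial metabolic response. Someone who continues to PET8 has that chance; someone who stops at PET4 has no PET8. Sites following different parts of the protocol would therefore give similar IR patients different chances of being counted as responders.

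**Working it through.** **Step 1: does IR fall under the rule in section 8.2?** Section 8.2 divides PET4 results into three: negative, progression, and Deauville 4-5 without evidence of progression. Appendix 3 defines IR as score 4 or 5 with increased uptake or lesion growth "occurring in the context of lack of overall progression (<50% increase) of overall tumour burden". The score excludes the negative branch, and the lack of overall progression separates IR from progressive metabolic disease. That leaves the third branch, in which the patient receives four more cycles. This is an inference from the definition, because section 8.2 does not use the term IR.

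**Step 2: compare the rules.**

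| Place | IR named? | Rule at PET4 | Conditions |
|---|---|---|---|
| Appendix 3, IR definition | Yes | Remains on treatment | None |
| Sections 8.2, 1.1 and 2.1 | No (by implication) | Will have four more cycles (section 2.1: up to four) | None beyond no progression |
| Appendix 3, IR management | Yes | May continue | Five |
| Section 3 | No | Only partial or no metabolic response listed | None stated |

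**Step 3: do the general safety rules make the five conditions redundant?** Only in part. Section 8.4 delays treatment for most drug-related toxicity of grade 3 or above and allows it to resume after recovery to grade 1 or baseline. Section 8.5.1.4 allows a restart after a grade 3 rash resolves. The fourth IR condition looks back at whether such toxicity has occurred. An IR patient with a resolved grade 3 rash could therefore continue under sections 8.2, 8.4 and 8.5.1.4, yet might fail the IR condition. Outside the IR management text, nothing at the PET4 decision asks for the compression check or the documented consent discussion.

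**Step 4: what happens to an IR patient who stops at PET4?** Section 9.5 lists end-of-treatment assessments for withdrawal in cycles 1-3, for complete response or progression after cycle 4, for withdrawal in cycles 5-7, and for completion of eight cycles. IR with stopping at PET4 fits none of these, so no further centrally reviewed scan is scheduled. Appendix 3 backdates confirmed progression to the IR date and confirms it at PET8 against PET0. It does not say how this works without a PET8.

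**Step 5: scale for the endpoint.** Inputs from section 18.1: null rate 0.40, target rate 0.60, 80% power, one-sided alpha 0.1, 30 patients, 16 responses. For X binomial with n = 30:

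- P(X ≥ 16 | 0.40) = 0.0971
- P(X ≥ 16 | 0.60) = 0.8246

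The stated design reproduces. One patient changes the rate by 1/30 = 3.3 points; 15/30 = 50.0% and 16/30 = 53.3%.

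The protocol gives no IR rate, no proportion of IR patients who would fail a condition, and no later response rate in IR. Purely as an assumption, suppose m of 30 expected responders are lost because IR patients do not reach PET8, so that the true rate is 0.60 − m/30. The probability of at least 16 responses is then 0.825 (m = 0), 0.711 (m = 1), 0.574 (m = 2) or 0.428 (m = 3). This shows sensitivity to single patients; it does not estimate m.

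**The case against.** The best defence is that the two parts of Appendix 3 can be read together. The sentence in the IR definition mainly concerns counting and says that IR is not in itself a reason to stop; the management text then supplies the specific rule. That is a fair reading of Appendix 3 alone. It does not reach section 8.2, which has no pointer to the conditions at the PET4 decision. It can also be argued that growing lesions are some evidence of progression, which would take IR out of the 8.2 branch. That is possible, but the IR definition rests on lack of overall progression, and a site should not have to settle the point.

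Several stronger readings are tempting and are not supported:

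- **That several sections name IR and continue it unconditionally.** Only the IR definition does so. Sections 8.2, 1.1 and 2.1 reach IR by implication, and section 3 omits it.
- **That IR patients would be treated without safeguards.** Section 8.2 holds cycle 5 until the central PET4 report arrives. Section 8.4 delays or stops treatment for toxicity and lets the investigator stop early, and section 15.1 allows withdrawal in the patient's interest. These overlap with the conditions on PI judgement and toxicity. The five conditions are also not all safety checks.
- **That the response status of an IR patient who stops is undefined.** Appendix 3 counts IR as a response only if a complete or partial response follows, and section 18.2.1 keeps all eligible treated patients in the denominator. That patient is a non-responder.
- **That PFS is undefined without PET8.** Sections 9.6.2, 9.7 and 12.5.2 still capture progression through follow-up and local confirmation, and section 18.2.2 defines PFS. Finer dating rules may sit in an analysis plan that is not shown. The gap in the protocol is confined to the backdating rule.

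**Conclusion.** The inconsistency is real and lies in current text. An unconditional statement in Appendix 3, and an unconditional rule in section 8.2 that covers IR by implication, stand against a five-condition rule elsewhere in Appendix 3 and a list in section 3 that leaves IR out. The practical consequence is that a site following section 8.2 could continue an IR patient without the compression check and the documented consent discussion.

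The effect on the response rate is real in kind but unknown in size: 3.3 points per patient, with no stated IR rate from which to say how many patients are involved. The conclusion assumes that IR belongs to the branch of positive scans without progression, which follows from its definition. No view is taken on which clinical rule is right. This should be corrected, but it does not undermine the design.

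**What to change.** Reconcile sections 1.1, 2.1, 3 and 8.2 and both parts of Appendix 3 so that they state one rule for IR at PET4. The clinical team chooses the rule. Section 8.2 should name IR and cross-refer to the place where the rule is set out. In Appendix 3, state how backdating of confirmed progression to the IR date applies to an IR patient who stops at PET4 and has no PET8. Nothing needs adding on responder counting, which is already settled.

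The cost is an amendment to wording in these places, with no extra procedures, patients or analyses.
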